### **Analysis methods**

The 90% confidence intervals for the proportion of responders at Day 85 in the LFG316 as well as the 90% confidence interval for the difference in response rates will be reported. The response rates at other time points (e.g., at Days 15, 29, 57) will be analyzed similarly.

Summary statistics for the secondary endpoints and their changes from baseline will be provided by treatment group and visit/time. A longitudinal analysis of the secondary PD endpoints may be performed if deemed relevant. Graphical displays of mean time profiles may be constructed as appropriate.

Descriptive statistics of safety data will be provided by treatment group. Adverse events will also be analyzed by treatment group. Ocular adverse events will be separately listed and analyzed by study eye vs. fellow eye.

## Assessment schedule

Study phase	J g> C u en	Treatment Period							Treatment extension for LFG316 Responders		C.....,C.		
		Day 1 - 14 lo -1	Day 1 Day 2 (+1 day)	Day 8 (±1 day)	Day 15 (+/-1 -bv)	Day 29 (+/-3 -bvsl)	Day 43 (+/-3 days)	Day',! (+/-3days)	Day 85" (± 3 days )	PRN	Day 169 (+/-5 days)	PRN	Day253 (+/-5 davsl)
Visit flumbers	5	N 5	M 5	*** 5	*** 5	.. 5"	.. 5	.... 5	*** 5"	Visit 9 or 777	.. 5	.. 5	.. 5
Informed Consent	X												
Corporate Confidential Information	X												
Inclusion /Exclusion criteria	X												
Relevant medical history / Current medical conditions	X												
Den-vv>r nhv	X												
Ocular history	X												
ECG	X								X				X
Alcohol and HIV history	X												
Ak:ohol abuse and dn deoendence history	X												
Smokino hist= *	X												
Physical exarrination	X								X				X
Laboratory Safety Tests; incl hematology, blood cherristry and urinalysis	X								X				X
P*** nancv test (obtained ore-dose)	X(serum	X (urine)			X (urine)		X (urine)	X (urine)	X (urine)	X (urine)	X (urine)	X (urine)	X (urine)
Roctv hei<Jht	X												
Roctv V.eiaht	X								X	X	X	X	X
II-xIV .....,,ture	X	X	X	X	X	X	X	X	X	X	X	X	X
Blood pressure / Pulse rate	X	X	X	X	X	X	X	X	X	X	X	X	X
Study co etion information													X
Comments	X	X	X	X	X	X	X	X	X	X	X	X	X
ACM!rse Ew nts (captured following initial dose administration)	X	X	X	X	X	X	X	X	X	X	X	X	X
SAEs (captured upon signing ICF until 4 weeks following final 'Asit)	X	X	X	X	X	X	X	X	X	X	X	X	X
Concomitant medsf Therapies	X	X	X	X	X	X	X	X	X	X	X	X	X
LFG316 Intra"real Dose administration(sh.fv <Ne only!>-A		X				X		X	X'	X'	X'	X'	x 2,J
P K sa ecollection (pre-dose)		X	X		X	X	X	X	X	X	X	X	X
PD /total C51 samnt<> collection Cor e-dose!		X	X	X	X	X	X	X	X	X	X	X	X
Corporate Confidential Information									-,-	-,-	-,-	-,-	-,-

## Corporate Confidential Information

**Ocular Assessment schedule**

Corporate Confidential Information

Study phase	Screening Visit	Treatment Period								End of Study (EOS) 	Corporate Confidential Information			
		D-14 to -1	Day 1	Day 2 (+1)	Day 8 (+1)	Day 15 (+/-1)	Day 29 (+/3)	Day 43 (+/3)	Day 57 (+/-3)		PRN	Day 169 (+/-5 days)	PRN	Day 253 (+/-5 days)
Visit Numbers	Visit 1	Visit 2	Visit 3	Visit 4	Visit 5	Visit 6	Visit 7	Visit 8	Visit 9 or 777		Visit 10		Visit 11	
Best corrected visual acuity (ETDRS)	OU 	OU	OU	OU	OU	OU	OU	OU	OU	OU	OU	OU	OU	
Intraocular pressure(IOP)	OU	OU 	OU	OU	OU	OU 	OU	OU 	OU 	OU 	OU 	OU 	OU 	
;;,n lamp oiomicroscopy	OU	OU	OU	OU	OU	OU	OU	OU	OU	OU	OU	OU	OU	
Spectral domain ocular coherence tomography (sd-OCT)	OU	OU				OU		OU	OU		OU		OU	
Dilated ophthalmoscopy	OU	OU 	OU 	OU 	OU	OU 	OU	OU 	OU 	OU 	OU 	OU 	OU 	
Color fundus photo	OU					OU		OU	OU	OU	OU	OU	OU	
Standardized Vitreous Haze Score	OU	OU	OU	OU	OU	OU	OU	OU	OU	OU	OU	OU	OU	
Anterior Chamber cells	OU	OU	OU	OU	OU	OU	OU	OU	OU	OU	OU	OU	OU	
Chorioretinal lesions (absent/present per PI)	OU	OU	OU	OU	OU	OU	OU	OU	OU	OU	OU	OU	OU	
Macular edema due to u iti s (absent/present per PI)	OU	OU	OU	OU	OU	OU	OU	OU	OU	OU	OU	OU	OU	

**Corporate Confidential Information**

1. OU--both eyes and all assessments will be done pre-dose

PI: Principal Investigator

2. Patients receiving LFG316 will have dilated ophthalmoscopy to verify perfusion of the retinal vessels in the study eye immediately after each LFG316 injection. IOP should be checked approximately 30 minutes following each LFG316 intravitreal injection in the study eye (SE).

## Corporate Confidential Information

## 1 Introduction

### 1.1 Background

Uveitis refers to approximately 25 different disorders characterized by the presence of intraocular inflammation. The major causes of uveitis are infections, systemic immune-mediated disease and autoimmune syndromes confined primarily to the eye (Pan et al 2014). These diseases are not confined to the uveal tract, comprised of the iris, ciliary body and choroid, but may also include the retina, retinal vessels and other structures (Jabs 2008). Uveitis is the 5th leading cause of visual impairment and blindness in the United States (Pan et al 2014) and responsible for 10% of blindness worldwide (Jabs 2008). Epidemiological studies reported that the incidence of uveitis in the general population varies between 17 and 52 cases per 100,000 people per year with a prevalence of approximately 38 to 714 cases per 100,000 in the population (Miserocchia et al 2013).

In Western countries, anterior uveitis accounts for at least 50% of all cases of uveitis, posterior uveitis for 15-30% (Wakefield and Chang 2005), and intermediate and panuveitis for the balance. The conventional treatment for non-infectious intermediate-posterior and panuveitis includes local and systemic corticosteroids with or without the addition of corticosteroid-sparing immunomodulatory therapy. Although these therapeutic options are effective in suppressing the inflammation, drug related co-morbidities and toxicities limit the use.

Noninfectious uveitis is thought to result from inappropriate activation of the immune system and is often associated with systemic autoimmune or autoinflammatory diseases, however when no such disease is present these cases are termed idiopathic. Considering the immune mediated nature of uveitis, corticosteroids are typically the first line of therapy for noninfectious uveitis. The route and dose of corticosteroids depend on the severity of the uveitis and whether the ocular inflammation is confined to the anterior segment (ie, anterior uveitis or iritis), the posterior segment (ie, intermediate-, posterior-uveitis) or both (ie, panuveitis). Local steroids, which often cause glaucoma and cataract, can be attempted, but systemic steroids are usually necessary to control the disease. Many cases of uveitis are not controlled with corticosteroids alone, or the dose of corticosteroids required to persistently suppress inflammation is higher than the Cushing threshold (about 8-10 mg prednisone equivalent/day). In such cases, one or more steroid-sparing immunosuppressive drugs are used, many of which are used off-label. Many of these steroid sparing therapies, including the commonly used methotrexate, take weeks to achieve full efficacy. Cyclosporine has a more rapid onset of activity, but at therapeutic levels is commonly associated with other co-morbidities such as nephrotoxicity and hypertension, requiring frequent monitoring. Thus, there is an unmet need for highly effective rescue therapy for patients with acute or relapsing disease, precluding the need for high dose corticosteroid therapy or prolonged systemic biologic therapy (Haziolan and Pleyer 2013).

The complement system is part of the innate immune defense mechanism and is involved in modulating various immune and inflammatory responses (Yang et al 2012). Within the eye, complement plays an important role in the generation and maintenance of tolerogenic/suppressive antigen-presenting cells (APCs). By regulating the production/expression of immune mediators, the complement system is required to mount the antigen specific CD4+ T-cell-mediated immune responses that cause inflammation in the eye (Jha et al 2010). Recent studies have demonstrated that complement system activation is critical for the development of autoimmune uveoretinitis. Both local (intravitreal) and systemic suppression of the host's complement system with an anti-CS antibody was shown to completely inhibit the development and progression of an antigen specific T-cell mediated murine model (experimental autoimmune uveitis, EAU) of intraocular inflammation (Copland et al 2010).

Under normal conditions, the complement system is active at baseline level and tightly regulated by various complement regulatory proteins (CRegs) such as complement factor H (CFH). CFH is one of the most important regulators in the alternative complement pathway and is involved in the pathogenesis of immunological diseases. Recent studies suggested that variants in the CFH gene are associated with several immune-mediated diseases. Activated complement, due to loss of CRegs regulation by CFH, might cause self-tissue damage in sensitive organs like the eyes. *In vivo* studies have revealed that human RPE cells can synthesize and express CFH, and upregulated secretion of CFH by RPE can suppress the development of EAU (Yang et al 2012). In previous studies by Yang and Ng, it has been found that polymorphisms in the *CFH* gene are associated with the development of neovascular age-related macular degeneration (AMD) as well as anterior uveitis in females (Yang et al 2011; Ng et al 2008). In addition, *CFH* polymorphisms have also been found to be associated with other immune-mediated diseases such as multi-focal choroiditis, hemolytic-uremic syndrome (HUS) and glomerulonephritis.

In patients with non-infectious intermediate and posterior uveitis, an association with the specific rs800292 (CFH 184 G/A) polymorphism was identified and showed a recessive effect (GG/AG versus AA genotype; odds ratio (95% CI) was 2.74 (1.13-6.62)). In addition, the frequency of carriers of the G allele was significantly higher in uveitis patients than in controls (Yang et al 2012). This information, combined with non-clinical EAU results and the considerable unmet need in noninfectious uveitis, has prompted the hypothesis that complement inhibition will be beneficial in this patient; the present study will test this hypothesis.

### **1.1.1.1 Relevant data summary**

Corporate Confidential Information

Corporate ConfidentialInformation

**Table 1-1 LFG316 Completed Studies**

Study	Design	Route of Administration	Doses	N
Corporate Confidential Information				
CLFG316A2102	A single-ascending dose Safety and tolerance, PK/PD study in age-related macular degeneration	IVT	Corporate Confidential Information	24; 24 LFG316
CLFG316A2201	A multiple dose Safety and tolerance PK/PD study in neovascular age- related macular degeneration	IV		4; 4 LFG316
CLFG316A2202	Multiple dose Safety and tolerance PK/PD study in neovascular age- related macular degeneration	IVT		45; 30 LFH316 15 Sham

**Corporate Confidential Information**

# Corporate Confidential Information

## CLFG316A2102

This was a single ascending dose study conducted to assess the safety and tolerability, as well as PK and PD of **intravitreally** administered LFG316 in patients with advanced AMD.

### Corporate Confidential Information

Overall, There were no drng related adverse events, deaths, serious adverse events, or discontinuations. [Table 1-3](#) below summarizes the top 5 most frequently reported adverse events observed in this study. Conjunctival hemorrhage was the most frequently reported ocular AE which can be attributed to the intravitreal injection procedure. None of the AEs were dose dependent or suspected to be related to the study drng. There was no increase in total CS or inhibition of alternative complement pathway activity. Anti-LFG316 antibodies were not detected in this study. The remaining safety assessments (e.g. vital signs, ECG, etc) and ocular assessments showed no clinically significant changes.

**Table 1-3 Adverse events by treatment condition from study CLFG316A2102 (n=24)**

	Corporate Confidential Information				
	LFG316 N=6	LFG316 n (%)	LFG316 N=6	LFG316 n (%)	Total N=24
Patients with AE(s)	6 (100)	6 (100)	3 (50)	4 (67)	19 (79)
Conjunctival haemorrhage	2 (33)	5 (83)	2 (33)	2 (33)	11 (46)
Eye pain	2 (33)	0	1 (17)	2 (33)	5 (21)
Eye irritation	1 (17)	2 (33)	1 (17)	0	4 (17)
Lacrimation increased	1 (17)	1 (17)	1 (17)	0	3 (12)
Vitreous detachment	1 (17)	0	0	1 (17)	2 (8)

Source: CLFG316A2102 CSR, Table 14.3.1-1.1

## CLFG316A2201

This study was a multicenter, multiple dose, 2-cohort trial to assess the safety, tolerability, pharmacokinetics, pharmacodynamics, and efficacy of intravenous (IV) LFG316 in patients with neovascular age-related macular degeneration. Novartis terminated this study and stopped recruitment after 4 subjects had been randomized to the c.....Camda.ml.... treatment arm. The decision to terminate the study was not due to any safety signal with LFG316. It was based upon a consideration of the reported number of patients with meningococcal infection and unclear risk of death due to meningitis noted after repeated dosing with Soliris® (Eculizumab), which is an approved antibody against complement factor 5 (C5) for the treatment of atypical hemolytic uremic syndrome and atypical hemolytic syndrome. See [Table 1-4](#) for a summary of adverse events.

**Table 1-4 Summary of Adverse Events from CLFG316A2201**

	10 mg/kg LFG316 N=4
Patients with at least 1 AE	4 (100)
Anaemia	1 (25)
Eye pain	1 (25)
Lacration increased	1 (25)
Photophobia	1 (25)
Visual acuity reduced	1 (25)
Vitreous detachment	1 (25)
Vitreous floaters	1 (25)
Otitis media	1 (25)
Diabetes mellitus	1 (25)
Chronic obstructive pulmonary disease	1 (25)
Dyspnea	1 (25)

Source: CLFG316A2201 CSR, Table 14.3.1-1.1

## CLFG316A2202

This study was a repeat-dose Proof-of-Concept study in patients with neovascular (wet) AMD. This study used a multicenter, randomized study design to assess the efficacy, safety, tolerability, and serum pharmacokinetics of 3 successive doses of intravitreally administered LFG316. Forty-five (45) subjects were randomized in a 2:1 ratio to either LFG316 ".....intravitreal injection (30 subjects) or to sham injection. There were no differences between the 2 treatment arms in the rate or use of rescue therapy with anti-VEGF on Day 85: the number of subjects who required anti-VEGF rescue therapy was 18 (62.1%) and 10 (66.7%) in the LFG316 and sham-injection arms, respectively. The mean ( $\pm$  SD) anti-VEGF rescue therapy rate up to Day 85 was 0.10 ( $\pm$  0.097) and 0.08 ( $\pm$  0.078) retreatment per week in the LFG316 and sham-injection arms, respectively (15 subjects) for total of 3 doses.

fu patients with neovascular (wet) AMD, monthly treatment with LFG316 eo,p.m.c., IVT was well tolerated with similar safety profile in both treatment groups. None of the AEs resulted in discontinuation from the study. No deaths or drug-related SAEs were reported. See [Table 1-5](#) and [Table 1-6](#) for Systemic and Ocular Adverse Events respectively.

**Table 1-5 System Organ Class and Adverse Events Observed in CLFG316A2202**

	LFG316 N=30	Sham N=15	Total N=45
	n(%)	n(%)	n(%)
Patients with at least 1 AE	16 (53.3)	9 (60)	25 (55.6)
Infections and infestations	6 (20)	4 (26.7)	10 (22.2)
Injury, poisoning, and procedural complications	5 (16.7)	1 (6.7)	6 (13.3)
Gastrointestinal disorders	3 (10)	3 (20)	6 (13.3)
Vascular disorders	2 (6.7)	3 (20)	5 (11.1)
Investigations	3 (10)	2 (13.3)	5 (11.1)
Nervous system disorders	3 (10)	1 (6.7)	4 (8.9)
Musculoskeletal and connective tissue disorders	2 (6.7)	2 (13.3)	4 (8.9)
Metabolism and nutrition disorders	2 (6.7)	1 (6.7)	3 (6.7)
Immune system disorders	2 (6.7)	1 (6.7)	3 (6.7)
General disorders and administration site conditions	2 (6.7)	1 (6.7)	3 (6.7)
Cardiac disorders	1 (3.3)	2 (13.3)	3 (6.7)

Source CLFG316A2202 CSR Table 14.3.1-1.1

**Table 1-6 Incidence of Ocular Adverse Events Observed in Subjects in CLFG316A2202**

	LFG316 N=30	Sham N=15	Total N=45
	n(%)	n(%)	n(%)
Patients with at least 1 AE	10 (33.3)	4 (26.7)	14 (31.1)
Conjunctival haemorrhage	6 (20)	1 (6.7)	7 (15.6)

Source CLFG316A2202 CSR Table 14.3.1-1.3

### CLFG316A2203:

This is a two-part (A and B) study;

#### CLFG316A2203-Part A

Part A is an ongoing, multicenter, double masked, randomized, multiple dose study to assess the efficacy, safety, tolerability, and serum pharmacokinetics of intravitreally administered LFG316 (5 mg) in subjects with geographic atrophy. Part A of the study has recruited the planned number of patients (n = 150), all of whom were randomized to receive monthly intravitreal LFG316 or sham (2:1 respectively) for 18 months. The cut-off date for the following safety report is 8th of May 2015.

**Serious adverse events:** During this study, 5 deaths (4 in the LFG316 treatment arm, 1 in the sham control group) have been reported and are tabulated below (See [Table 1-7](#)).

#### Adverse Events:

The most common non-ocular AEs were upper respiratory tract infection which occurred in 17 subjects (11.3%) and hypertension which occurred in 13 subjects (8.7%), followed by nausea, pharyngitis and bronchitis in 12 subjects each (8%). None of the AEs were deemed to be related to the study medication.

The most common ocular AE was conjunctival hemorrhage which occurred in 99 subjects (66%), followed by vitreous floaters (25 subjects; 16.7%), eye pain (19 subjects; 12.7%), foreign body sensation (17 subjects; 11%), and eye irritation (16 subjects; 10.7%). Two subjects discontinued due to developing moderate choroidal neovascularization in the

study eye. None of the AEs were deemed to be related to the study medication. Instead they were deemed to be related to the study procedure.

## Corporate Confidential Information

### **1.2 Study purpose**

The overall purpose of this study is to assess whether intravitreal LFG 316 reduces intraocular inflammation in patients with active non-infectious intermediate-, posterior-, or panuveitis (NIU) who require intensification of systemic immunosuppressive therapy. If positive, the results would enable development of a more effective and specific therapy for various forms of NIU.

## 2 Study objectives

### 2.1 Primary objectives

To assess the effect of intravitreal LFG316 Corporate Confidential Information on the protocol-defined, Day 85 response rate in eyes of patients who meet the inclusion criteria

The above objective applies to the study eye only. A response will be defined by any **one** of the following criteria in the study eye:

- An improvement of 2 or more steps in vitreous haze, relative to baseline. For the purpose of "step" calculation, 0.5 shall count as one of the increments. Thus, improvement from a score of 2 to 0.5 or from 1 to 0 would constitute a 2-step improvement, or
- An improvement of 10 or more letters in visual acuity, relative to baseline, or
- An improvement of 2 or more steps in anterior chamber cells score, relative to baseline or
- Absence of chorioretinal lesions as determined by the investigator
- Change in central retinal thickness from baseline to Day 85 of 50 micrometer

Remission (complete response) will be defined as any patient who has a vitreous haze score of 0 or 0.5 and who has an anterior chamber cell score of 0 and no chorioretinal lesions in the study eye and is off all immune modulatory therapy (systemic, corticosteroids and topical), without any worsening of uveitis during the trial.

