**Concomitant medications/Significant non-drug therapies:**

Intravitreal administration involves certain protocol-specified anesthetics and antibiotics. See the full protocol for a complete list of concomitant, permitted, and prohibited medications.

Corporate Confidential Information

**Primary endpoint:** response rate at Day 85, LFG316 treatment arm.

A response will be defined by any one of the following criteria in the study eye:

- An improvement of 2 or more steps in vitreous haze, relative to baseline. For the purpose of "step" calculation, 0.5 shall count as one of the increments. Thus, improvement from a score of 2 to 0.5 or from 1 to 0 would constitute a 2-step improvement **or**,
- An improvement of 10 or more letters in visual acuity, relative to baseline **or**
- An improvement of 2 or more steps in anterior chamber cells, relative to baseline **, or**
- Resolution of chorioretinal lesions as determined by the investigator, **or**
- Change in central retinal thickness from baseline to Day 85 of 50 micrometer

Remission (complete response) will be defined as any patient who has a vitreous haze score of 0 or 0.5 in the study eye, who has an anterior chamber cell score of 0 and no chorioretinal lesions in the study eye and is off all immune modulatory therapy (systemic, corticosteroids and topical), without any worsening of uveitis during the trial.

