### 4.1 Inclusion criteria

Patients eligible for inclusion in this study must fulfill **all** of the following criteria:

1. Written informed consent must be obtained before any assessment is performed.
2. Male or female patients 18 years or older.
3. Active NIU, in at least one eye, as defined below, in patients requiring intensification of systemic immunosuppressive therapy:
  - Vitreous haze of at least 1+ at screening on the scale of [Nussenblatt et al 1985](#), or
  - Chorioretinal lesions due to uveitis (chorioretinal lesions due to infectious uveitis are excluded)
  - Patients who present with a flare and who are at the time of the emollement on systemic corticosteroid or non-steroidal immunosuppressants will have their therapy tapered or stopped, respectively, at the time of intravitreal LFG316 administration.
4. ETDRS visual acuity of 20 letters (20/400) or better in the study eye.
5. Women of child-bearing potential (WOCBP), defined as all women physiologically capable of becoming pregnant, unless they are using effective methods of contraception during dosing of study treatment and 7 weeks (5 times the terminal half-life) of LFG316.

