### 6.4.3 Chorioretinal lesions

Chorioretinal lesions will be assessed as present or absent by the investigator

Corporate Confidential Information

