## 2 Study objectives and design

### 2.1 Study objectives

#### 2.1.1 Primary objective(s)

- To assess the effect of intravitreal LFG316 Corporate Confidential Information on the protocol-defined, Day 85 response rate in the study eye of patients who meet the inclusion criteria.

The above objective applies to the study eye only.

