**Handling of missing values/censoring/discontinuations**

If a subject had missing data for any of the parameters needed to derive the responder status, a subject was:

- Considered as a responder if the subject met any of the responder criteria
- Considered as missing if all the parameters for the responder criteria were missing
- Considered as a non-responder, if the subject had at least one non-missing parameter needed for the responder criteria and had met no criteria to be considered a responder.

If a subject had missing data for any of the parameters needed to derive the remission status, a subject was:

- Considered as a remission if the subject met all of the remission criteria.
- Considered as a non-remission, if the subject did not meet at least one of the remission criteria.
- Considered as missing, if the subject met all the available remission criteria but not all the remission criteria were available.

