Percentage of patients that respond per response criterion (for criterion involving central retinal thickness, only if applicable) will be reported in each treatment group.

A separate set of summary tables will be produced for those subjects who participate in the LFG316 treatment extension, if deemed necessary.

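### The primary Day 85 response is listed differently in Protocol 2.1, the synopsis and SAP 7.1; the live conflict for the reported rate is whether a retinal thickness change counts

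*Protocol*

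**What the plan says.** All three lists define a response as any one criterion met in the study eye. They agree on vitreous haze (2 or more steps), visual acuity (10 or more letters) and anterior chamber cells (2 or more steps), each relative to baseline. They differ on the rest.

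- **Protocol 2.1** adds "Absence of chorioretinal lesions as determined by the investigator" and "Change in central retinal thickness from baseline to Day 85 of 50 micrometer": five criteria.
- **Protocol synopsis, primary endpoint** adds "Resolution of chorioretinal lesions as determined by the investigator" and the same thickness item: five criteria.
- **SAP 7.1** adds the resolution item in the synopsis wording and then goes straight to remission: four criteria, no thickness.

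Protocol 9.4.1 does not restate the definition. SAP 2.1.1 gives the objective as the effect "on the protocol-defined, Day 85 response rate in the study eye of patients who meet the inclusion criteria". SAP 7.2.1 plans a summary of response per criterion that still allows for thickness: "for criterion involving central retinal thickness, only if applicable". No visible text says which list governs.

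**The concern.** The same patient can be a responder under one document and a non-responder under another, on the primary endpoint. The missing-data rule in SAP 7.1 makes this a full switch. A patient who meets none of the SAP's criteria is "Considered as a non-responder, if the subject had at least one non-missing parameter needed for the responder criteria", so someone who qualifies only by thickness is not set aside as missing but counted as a failure.

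The lesion wording raises a separate problem. Entry is possible on haze alone ("Vitreous haze of at least 1+ at screening on the scale of" is one of two alternatives in Protocol 4.1), and "Chorioretinal lesions will be assessed as present or absent by the investigator". A study eye can thus have no lesions at baseline. *Absence* is a state at Day 85 and names no baseline, so such an eye would count as a response with no improvement in anything.

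At stake is what the reported rate means: SAP 7.1 as written estimates something other than the rate defined in Protocol 2.1. Investigators, patients and the sponsor know the assignment (Protocol 5.4), so a choice among the lists made late could be made with results in view.

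**Working it through.** **1. The lists side by side.** Status of a study eye at Day 85, with other response parameters recorded:

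| What the eye meets | Protocol 2.1 (literal) | Synopsis | SAP 7.1 |
|---|---|---|---|
| Haze, acuity or anterior chamber criterion | Responder | Responder | Responder |
| Lesion at baseline, none at Day 85, nothing else | Responder | Responder | Responder |
| Thickness item only | Responder | Responder | **Non-responder** |
| No lesion at baseline or Day 85, nothing else | Responder | **Non-responder** | **Non-responder** |

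The lists are nested. Resolution implies absence at Day 85, and adding an item to an any-one list can only add responders. So the count under SAP 7.1 is at most that under the synopsis, which is at most that under literal Protocol 2.1. A patient's status changes only if no other criterion is met.

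**2. Which difference is live.** SAP 7.1 is the list the analysis will follow. It agrees with the synopsis on the lesion item, so row 4 affects the reported rate only if Protocol 2.1 is applied. Row 3 separates the SAP from both protocol lists.

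**3. Size per patient.** Inputs: n = 16 planned for LFG316 and a 60% reference rate (synopsis, sample size; SAP 7.1), with a 90% Clopper-Pearson interval (SAP 7.1).

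Step per patient = 100/16 = 6.25 points. With fewer evaluable patients it is larger; at 14, for example, 100/14 = 7.1.

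For x responders of n, the limits are: lower = 5th percentile of Beta(x, n − x + 1); upper = 95th percentile of Beta(x + 1, n − x).

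| Responders | Rate | 90% exact interval |
|---|---|---|
| 9/16 | 56.25% | 33.3 to 77.3 |
| 10/16 | 62.5% | 39.1 to 82.2 |
| 11/16 | 68.75% | 45.2 to 86.8 |
| 12/16 | 75.0% | 51.6 to 91.0 |

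The documents do not say how many patients would qualify by thickness alone or by literal absence alone. The table is an assumed illustration: 9/16 under the SAP list, then 0, 1, 2 or 3 patients reclassified. All four intervals contain 60%.

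**4. The plan's own figures.** The synopsis states a 17% false positive rate and power of 45%, 80% and 92% for rejection at 11/16. Exact binomial tails give 32.9% and 66.0%, 91.8% and 97.7% for 11 or more, and 16.7% and 45.0%, 79.8% and 92.1% for 12 or more. The stated figures therefore belong to 12 or more. That is a separate matter, and nothing above depends on it.

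**The case against.** The strongest reply is that there is one operative list. The SAP will be programmed, it matches the synopsis on lesions, and *absence* in Protocol 2.1 may be loose wording for *resolution*. This stands in part: a reader might infer that the absence wording inflates the rate the SAP will report, and the documents do not support that. The wording in Protocol 2.1 still needs correcting.

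Second, leaving out thickness may be deliberate. SAP 2.2 says the sd-OCT images are only quality-checked and archived, SAP 7.2.1 makes the thickness criterion conditional, and redacted text in SAP 1.2 and 7.1 may give a reason. That also stands, so the omission should not be called an oversight. But the visible response list shows no redaction, and a hidden reason cannot make the three lists identical or make the SAP's rate the protocol-defined one.

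Third, a starting count of 9/16 is convenient: one more responder takes the estimate past 60%, whereas from 10/16 upwards the estimate is already above it. A reader might infer that one patient could reverse the trial's conclusion. The documents do not support that. The SAP says no decision should rest on the p-value, the intervals shown all contain 60%, and the number reclassified may be zero.

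Finally, remission, also named as primary in Protocol 9.4.1 and SAP 7.1, has essentially the same definition in all three places and is not affected.

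**Conclusion.** The concern holds in this form: three different lists define the primary response, and no visible text says which governs. The thickness item is the live conflict, because it alone separates the SAP's reported rate from both protocol lists. The absence wording is a real defect confined to Protocol 2.1.

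The size is 6.25 points per reclassified patient, assuming all 16 planned LFG316 patients are evaluable. The direction is known: the SAP rate cannot exceed the protocol rate when the same patients are classified. The number of patients is not known and may be zero. The intervals are wide, 33.3 to 77.3 at 9/16 and 51.6 to 91.0 at 12/16, so within the range shown the reading against 60% does not change. The consequence is for the reported rate and its interval, and for whether they describe the endpoint the protocol defined, not for a decision.

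**What to change.** - **One list.** Put the same criteria, word for word, in the synopsis, Protocol 2.1 and SAP 7.1. Word the lesion item as *resolution of chorioretinal lesions present at baseline*.
- **Settle thickness.** Decide before any response data are reviewed, and no later than database lock, whether it is a response criterion. Either remove it from the synopsis list, Protocol 2.1 and the per-criterion summary in SAP 7.2.1, or add it to SAP 7.1 with the direction of change and *at least* stated. The public text shows neither; check the source document in case a symbol was lost in conversion.
- **Capture the values either way.** Mean change in central retinal thickness is a secondary endpoint in the synopsis. SAP 2.2 (images only checked and archived) and SAP 8 (sd-OCT results listed, possibly summarised) must be reconciled so that thickness values from the scheduled scans are recorded.

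**Cost.** A written protocol amendment with the approvals in Protocol 11.1, a new SAP version under SAP 1.2, and capture of values from scans already scheduled. The response rate may be lower than under the literal Protocol 2.1 list.
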